**Stopping Rules:**

IMG-7289 will be discontinued in the event of the following:

- Post DLT, the Principal Investigator deem it unsafe for the patient to continue on IMG-7289.
- Post dose reduction due to DLT, the patient either worsens at any time or fails to demonstrate significant improvement within 14 days.
- Post temporary interruption of IMG-7289 due to platelet counts below  $50 \times 10^9/L$  (50,000/ $\mu L$ ), the patient's platelet counts don't return to  $> 150 \times 10^9/L$  (150,000/ $\mu L$ ) within 21 days.
- Any Grade 4 non-hematologic adverse event with failure to recover to Grade 3 within 7 days of drug cessation.

**Study Design:** This study will follow a Simon two-stage design with an anticipated lower limit response rate of 10% and a target response rate of >40%. With these parameters, the optimal Simon design with  $\alpha=0.05$  and 90% power would need 9 patients in the first stage and 11 patients in the second stage. After testing oral IMG-7289 on 9 patients in the first stage, the trial will be terminated if 1 or fewer respond. If the trial goes to the second stage, a total of 20 patients will be enrolled. If the total number responding is less than or equal to 4, oral IMG-7289 will be rejected; if the total number responding is more than 4, oral IMG-7289 will be considered worthy of further study.

### 3 Background

#### 3.1 Background on the Disease to be Treated

The *BCR-ABL* 1-negative myeloproliferative neoplasms (MPNs) are a family of related neoplastic disorders of bone marrow. The three main chronic *BCR-ABL* 1-negative MPNs are polycythemia vera (PV), essential thrombocythemia (ET) and primary myelofibrosis (PMF). The cardinal clinical features of these disorders are increased red cell mass in PV, increased platelet count in ET, and bone marrow fibrosis in PMF. The MPNs are clonal disorders arising most frequently from acquired (somatic) mutations in a multipotent hematopoietic stem/progenitor cell, resulting in abnormalities in red cell, granulocyte and platelet production often in association with marrow fibrosis and extramedullary hematopoiesis and, in some cases evolution to acute myeloid leukemia (AML).

ET is an indolent hematologic cancer characterized by reduced quality of life, thrombocytosis, elevated cytokines, an increased rate of thrombosis and bleeding and the potential to develop myelofibrosis and acute myeloid leukemia (Vannucchi *et al.* 2017). Transformation to post-ET myelofibrosis and post-ET acute leukemia occurs at a rate of 4–11% and 2.1–5.3% at 15 years, respectively (Cerquozzi and Tefferi, 2015). Risk factors for poor survival include age over 60, leukocytosis, and a prior history of thrombosis (Barbui *et al.*, 2012). Indications for pharmacologic treatment in ET include extreme thrombocytosis, elderly age, *JAK2*V617F mutational status, and history of thrombosis or presence of cardiovascular risk factors (Rumi *et al.*, 2017). Standard first-line pharmacologic treatment to reduce thrombocytosis is hydroxyurea (HU) which has a low incidence of acute toxicity but is regarded by some as mutagenic. However, approximately 20–25% of ET patients will be resistant or intolerant of HU per ELN criteria and treatment with HU has been demonstrated to worsen symptom burden (Sever *et al.*, 2014; Geyer *et al.*, 2015). Thus, there remains **unmet need** for therapeutic interventions that reduce thrombocytosis and improve symptom burden among individuals with HU-resistant or intolerant ET per ELN criteria.

#### 3.2 Study Rationale

This is an open-label, single-arm, single-site Investigator Initiated Trial (IIT) of the LSD1 inhibitor, IMG-7289. ET is characterized by a neoplastic process expanding myeloid lineages including the erythroid progenitor and megakaryocyte populations, platelet production and leukocytosis. Growth factors and cytokines synthesized by megakaryocytes and granulocytes contribute to symptoms and to bone marrow fibrosis. The disease is described as a clonal disorder of hematopoietic stem/progenitor cells that have acquired a somatic mutation activating the JAK/STAT pathway. As such, the activated, proliferating megakaryocyte-erythroid progenitor and its mature progeny are the pathologic seat of the disease.

LSD1, also known as KDM1A, is an enzyme that removes mono- and dimethyl groups from histone (H) H3 at critical lysines (K), K4 and K9 (Shi *et al.*, 2004). Methylation of histone H3K4 and H3K9 is a post-translational modification associated with changes in the confirmation of chromatin (Bannister and Kouzarides, 2011; Beisel and Paro, 2011). Chromatin is a collective term for the association of nuclear macromolecules consisting of DNA, protein scaffolding, enzymes enhancing transcription and synthesis of RNA (Kornberg, 1974). The DNA and its protein scaffold of histones form an ordered complex called the nucleosome. Each nucleosome is composed of two copies of each of the four histone proteins, H2A, H2B, H3 and H4, forming an octamer around which DNA is wrapped. The rates of gene transcription are heavily influenced by the accessibility of transcription factors and the RNA polymerase complexes to template DNA at promoters (Bannister and Kouzarides, 2011; Beisel and Paro, 2011).

LSD1 enzyme activity is essential for the maturation of megakaryocytes and red blood cells from the megakaryocyte-erythrocyte progenitor (MEP) cell. In MEPs, LSD1 is recruited to chromatin *via* the transcription factor GFI1b, a protein also essential to MEP differentiation. Genetics studies have shown that interference with either *GFI1b* or *LSD1* has similar effects on the maturation of megakaryocytes and production platelets. Thus, therapeutically targeting LSD1 effectively reduces megakaryocyte numbers and the growth factors and cytokines that drive the secondary clinical effects observed in ET.

[figure not shown]
In myeloproliferative neoplasms including ET, LSD1 is overexpressed in myeloid cell lines including megakaryocytes and erythroid precursors (Niebel *et al.*, 2014). LSD1 inhibition has been found to be effective in inducing the apoptosis of human Janus kinase (JAK)2V617F cell lines, reducing inflammatory cytokines, reducing spleen volumes, decreasing bone marrow fibrosis, and reducing extramedullary hematopoiesis in *Mpl*W515L or *Jak2*V617F-mutated murine models. Additionally, LSD1 inhibition with IMG-7289 was shown in a *Jak2*V617F mouse model of ET/PV to selectively decrease the number of malignant megakaryocytes as well as reduce elevated platelets, red cells and granulocytes (Jutzi *et al.*, 2018). Toxicologic studies in rat and dog demonstrated a decreased red blood cell mass, platelet and neutrophil counts in a dose-dependent manner. LSD1 is known to participate in the maintenance of the self-renewal potential in stem/progenitor cells as well as enhance an interferon response in malignant cells. Whether the inhibition of LSD1 with IMG-7289 can gradually reduce the mutant cell burden as was observed in mice remains to be seen in patients.

Our proposed study is innovative in that it is the first study to determine the effects of IMG-7289 in a population of ET patients. This study will (a) provide data on the utility of IMG-7289 in the reduction of platelet counts in patients that have relapsed or are resistant to or intolerant of HU per ELN criteria, (b) determine the effects of IMG-7289 on disease-related markers including biomarkers and symptom burden with the aim of filling an unmet need in the management of ET.

At the doses proposed in this study, IMG-7289 is cleared in less than 24 hours allowing LSD1 activity to return and resume its function in normal hematopoiesis. Chronic daily administration of IMG-7289 in rat, dog and humans has been well tolerated. No safety signals have been observed in either the AML/MDS or myelofibrosis studies with IMG-7289 at doses up to 6 mg/kg/d.

### 3.3 Background on IMG-7289

LSD1 is a component of chromatin-modifying complex that alters the transcriptional activity of enhancers and transcription factors themselves (Rudolph *et al.*, 2013). Hematopoietic cells require LSD1 for stem cell maintenance and for progenitor differentiation in the granulopoietic, thrombopoietic, and erythropoietic lineages (Kerenyi *et al.*, 2013). In myeloproliferative neoplasms including ET, LSD1 is overexpressed in myeloid cells including megakaryocytes/ erythroid progenitors (Niebel *et al.*, 2014). LSD1 inhibition induced apoptosis in mutant stem/progenitor cells, reduced inflammatory cytokines, reduced spleen volumes, decreased bone marrow fibrosis, and reduced extramedullary hematopoiesis in *Mpl*W515L *JAK2*V617F-mutated murine models of MPNs (Imago Investigator Brochure). Long-term toxicologic studies in rat and dog demonstrated the expected pharmacodynamic effects of decreased red blood cell mass, platelet and neutrophil counts in a dose-dependent and reversible manner (Figure 1).

**Figure 1.** Dose-dependent decrease in platelet counts observed in male and female rats treated with IMG-7289 for 13 weeks.

### 3.4 Rationale for and Safety of the Proposed Starting Dose

The primary scientific goals of the study are to determine the hematologic effects of IMG-7289 in ET patients, and to establish the safety of dose titration based on periodic hematology evaluations and the impact of inhibiting LSD1 for a fraction of the dosing cycle (24 hours) sufficient to reduce the production of platelets.

The proposed protocol includes patients with ET who have failed at least one standard therapy (failure is the equivalent of inadequate response or intolerance). The therapeutic goal for the treatment of ET is to inhibit the activity of LSD1 in hematopoietic cells for only a fraction of the 24-hour dosing cycle, sufficient to reduce the production of platelets whose over-production characterizes the condition.

Considerations for a safe and therapeutic starting dose include chronic toxicology studies in conjunction with the clinical experience of the patients who have received IMG-7289 to date in IMG-7289-CTP-101 and -102. In the CTP-101 protocol, IMG-7289 was administered to patients with high-risk AML and MDS; the therapeutic thesis in that study was to completely inhibit LSD1 in all hematopoietic cells, recognizing patients would need clinical support for cytopenias. The starting dose was 0.75 mg/kg/d and the effective dose, at which no safety signals have been observed, was deemed 6.0 mg/kg/d. Though the great majority of the patients entered the study with Grade 3/4 thrombocytopenia, patients at all dose levels of IMG-7289 required platelet transfusions. This sensitivity of thrombopoiesis to LSD1 inhibition in high-risk AML/MDS patients reflects the generally compromised nature of the bone marrow, including the reduction of megakaryocytes, in that disease.

Taking this observation into account in association with the therapeutic goal for the treatment of myeloproliferative neoplasms -- inhibiting LSD1 activity in hematopoietic cells for only a fraction of the 24-hour dosing cycle -- and PK modeling, the original starting dose in the CTP-102 protocol for myelofibrosis patients was 0.25 mg/kg/d. Platelet counts in the first twenty patients ranged from 102 to 1039 k/ $\mu$ L and all required a dose increase to lower platelet counts. In a recent analysis of the ongoing IMG-7289-CTP-102 study in myelofibrosis patients, the daily dose of IMG-7289 needed by a majority of patients to achieve a platelet count in the target range (50-75 k/ $\mu$ L) ranged between 0.6 to 0.8 mg/kg/d with the full dosing spectrum of 0.4-1.5 mg/kg. The dose needed to reduce the platelet count to the target range in patients with myelofibrosis was *not* correlated with the starting platelet count or the antecedent hematologic history. Platelet counts in patients with ET will, on average, be significantly higher than those in patients with myelofibrosis who have failed treatment with the standard of care. Notwithstanding, the kinetics of changes in platelet counts in patients with ET treated with IMG-7289 are expected to be similar to those patients with myelofibrosis. Accordingly, to enable ET patients to reach the optimum dose sufficient to reduce platelets below 400 k/ $\mu$ L while still maintaining an adequate safety margin, an IMG-7289 starting dose of 0.6 mg/kg QD has been selected.

Collectively, these studies established some key points. First, inhibition of LSD1 for a fraction of the 24-hour dosing cycle can be achieved safely. Second, the platelet count can be targeted to a specific range by adjusting the dose of IMG-7289.

To meet the eligibility criterion for enrollment, ET patients must have a platelet count above 450 k/ $\mu$ L. The therapeutic target platelet count is between 200 and 400 k/ $\mu$ L. Based on previous clinical experience in patients (all with compromised hematopoiesis), a starting dose (Ds) of 0.6 mg/kg, or 42 mg QD for a 70 kg patient, is deemed safe in a patient population characterized by an excess of platelets. Dose adjustments in increments and decrements of between 0.2, 0.1 and 0.15 mg/kg will allow up- or down-titration of IMG-7289 to achieve the target platelet count (Table 1). Hematology assessments will ensure safety and guide dose adjustments, which may be made in accordance with the rules detailed in Section 6.2.

### 3.5 Justification of the Dose and Regimen

The phenotypic effects of LSD1 inhibition are mediated through changes in the gene expression patterns that are a consequence of transcriptional reprogramming that occurs in the absence of LSD1 activity (Harris *et al.*, 2012). The phenotypic consequences are cell-specific, include differentiation and, ultimately, cell death. In the primary pharmacology studies with IMG-7289, these changes take place over a period of days to weeks; in the assay for self-renewal potential (clonogenicity), these changes take days or weeks to observe. Complete and sustained inhibition of LSD1 may be the best strategy to rapidly reduce the leukemic stem cell burden in the case of AML; however, in less aggressive myeloid neoplasms such as ET, chronic treatment at doses that do not completely deprive the hematopoietic process of LSD1 activity is anticipated to be well tolerated while having a significant impact on disease. In mouse models of myelofibrosis, the gradual loss of cells bearing the MPN mutation (*Jak2* or *Mpl*) was observed over the course of modest LSD1 inhibition. What emerges from

these mouse studies is a therapeutic strategy that balances safety with clinical efficacy: inhibit the enzyme for only a fraction of the 24-hour dosing cycle to allow some normal thrombopoiesis to occur, thus preventing profound thrombocytopenia. At this stage of development, this optimal therapeutic dose must be identified in each patient because variations in the severity of disease and perhaps other factors will dictate the starting platelet count and hence, sensitivity to drug.

The safety of longer durations of treatment is supported by the 26 and 39-week toxicology studies in rat and dog, respectively. Treated animals in which thrombopoiesis is not completely inhibited show no observable irreversible adverse effects on hematopoiesis. The primary effects of LSD1 inhibition are confined to the bone marrow with expected secondary effects a consequence of cytopenias at higher doses.

Observations regarding dose-response in patients with MF treated in the CTP-102 study have led to modifications of the titration schedule. As additional patients have been treated, it has been noted that for a given daily dose, the platelet count continues to fall beyond Day 7 of dosing, i.e., two successive weekly up-titrations caused the platelet count to fall more than expected and occasionally led to significant thrombocytopenia. In those patients who had received an identical dose for 3 consecutive weeks, each experienced a drop (mean -31%; N=20) in the platelet count between Day 7 and Day 14. The mean decrease in platelet counts from Day 14 and Day 21, however, was approximately -12%, suggesting that a steady state of drug exposure, LSD1 activity and platelet production occurs between Day 21 and Day 28. As such, it appears that two or three weeks between up-titrations is an insufficient amount of time for both the plasma concentrations of the drug and platelet production to reach a new steady-state necessary to achieve a stable platelet count. Therefore, up-titrations may occur no more frequently than every four weeks from the previous up- or down-titration. Down-titrations can occur at any time in best interest of the patient.

At the doses proposed in this study, the concentration of IMG-7289 is sufficient to inhibit hematopoiesis for a fraction of the 24-hour dosing period, thus allowing LSD1 activity to return and resume its function in normal thrombopoiesis. Chronic daily administration of IMG-7289 in rat, dog and humans has been well tolerated. No safety signals have been observed in either the AML/MDS or myelofibrosis studies with IMG-7289 at doses up to 6 mg/kg/d. Please refer to the Investigator's Brochure for additional information on the non-clinical and clinical studies conducted to date with IMG-7289.

## 4 Statement of Study Objectives

### 4.1 Study Aims and Hypotheses

**Aim 1.** To assess the hematologic effects of IMG-7289 in a population of ET patients requiring platelet control who are resistant to or intolerant of hydroxyurea per ELN criteria.

**Hy1:** IMG-7289 will induce complete hematologic response in >10% of this study population by 24 weeks.

**Aim 2:** To qualitatively examine markers of disease burden including patient-reported symptom burden, standard ARUP testing of mutant (variant) allele burden in granulocytes (baseline and Week 24), spleen size, and bone marrow histology.

**Hy2:** ET patients treated with IMG-7289 will experience improved symptom burden, reduced mutation allele burden, improved spleen size if enlarged at baseline, and reduced megakaryocyte hyperplasia following the 24-week treatment course.

### 4.2 Endpoints

#### 4.2.1 Primary Endpoint

- Determine the proportion of patients who achieve complete hematologic remission at Week 24 using ELN response criteria for ET ([Barosi et al., 2013](#)), as per protocol appendix 12.4.

#### 4.2.2 Secondary Endpoints

- Determine the proportion of patients who achieve a reduction from baseline in TSS derived from the MPN-SAF at any time-point within the course of the 24-week study.
- Determine the proportion of patients who achieve a reduction in spleen length for patients with palpable splenomegaly (>5 cm below the left costal margin) at any time point over the course of the 24-week study.
- Among patients harboring a *JAK2*V617F mutation, determine the proportion of patients who achieve a >25% change in mutant allele burden from baseline to Week 24.
- Assess if there are changes in bone marrow histology between bone marrow biopsies at baseline and Week 24.

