◊ Patients requiring a dose hold should have complete blood counts monitored at least weekly for safety purposes and to enable re-challenge to commence as soon as counts return to the required level, if safe to do so.

\*The PI may, upon review of individual patients and patient responses, recommend up- or down-titrations that are not in concordance with the above.

\*\* Re-challenge at 50% of the previous mg/kg dose.

\*\*\* PRBC transfusions allowed if at 0.15 mg/kg/d down-titrated dose level transfusions requirement remains stable within 2 units per month, and no more than 4 units total per 28 days, and patient otherwise has evidence of clinical benefit.

‡ Upon re-challenge, all of the above rules reapply.

**Additional Treatment Period (ATP):** Qualifying patients will 're-start' IMG-7289 on ATP Day 1, with dose titration continuing as per the Titration Rules table above; there should be no interruption in dosing (i.e., Day 169 = Day 1 of new ATP). Additional dose-titration may occur in consultation with the Principal Investigator.

**Study Duration:** Screening procedures may commence up to 28 days prior to the start of treatment. Patients may initially receive up to 24 weeks of dosing while on study. Patients will be followed for 28 days post last dose. Therefore, the anticipated duration of participation in the study is expected to be approximately 32 weeks from first patient-first visit to last patient-last visit. Additional treatment may be given, contingent on an assessment of patient benefit for multiple repeating ATPs.

**Study Assessments:** The assessments outlined below are also summarized in Section 7 and in the Schedule of Assessments Sections 7.7 and 7.8.

The Myeloproliferative Neoplasm Symptom Assessment Form (MPN-SAF) will be completed at Screening (as close to Day -7 as possible) and once weekly from Day 1 through the End of Study (EoS) Visit (Appendix 12.6). Multiple questionnaires will need to be provided to the patient for completion as visit schedule decreases over time.

ECOG Performance Status will be performed at Screening, and on Days 85 and 169 of the ITP, on Day 169 of the ATP for as long as the patient continues to qualify, at EoT, EoS/ET, and upon suspicion of relapse.

Adverse events (AEs) will be assessed at every visit post first IMG-7289 dose through the EoS visit.

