## 10 Statistical Analysis

**Analytic Plan:** This will be a one arm Simon 2-stage design with up to N=20 subjects. Complete hematologic remission (primary outcome) and overall symptom burden (secondary outcomes) will be assessed at weeks 20 and 24 (response at Week 24 only).

**Sample Size and Power:** This study will follow a Simon two-stage design with an anticipated lower limit response rate of 10% and a target response rate of >40%. With these parameters, the optimal Simon design with  $\alpha=0.05$  and 90% power would need 9 patients in the first stage and 11 patients in the second stage. After testing oral IMG-7289 on 9 patients in the first stage, the trial will be terminated if 1 or fewer respond. If the trial goes to the second stage, a total of 20 patients will be enrolled. If the total number responding is less than or equal to 4, oral IMG-7289 will be rejected; if the total number responding is more than 4, oral IMG-7289 will be considered worthy of further study.

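### The TSS and spleen secondary endpoints count a fall of any size at any time point, so neither proportion can by itself support Hy2

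*Combined protocol and SAP*

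**What the plan says.** Section 4.2.2 lists two proportions of this kind. The symptom endpoint counts patients who "achieve a reduction from baseline in TSS derived from the MPN-SAF at any time-point within the course of the 24-week study". The spleen endpoint, restricted to patients whose spleen is palpable more than 5 cm below the costal margin, counts a reduction in length "at any time point over the course of the 24-week study". Neither has a minimum size, a confirmation rule or a durability rule.

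The Study Synopsis (Study Assessments) has the MPN-SAF completed at Screening and then "once weekly from Day 1 through the End of Study (EoS) Visit". Sections 7.2 and 7.3.1.1 therefore give two pre-dose forms, one near Day -7 and one on Day 1. Section 4.2.2 does not say which is baseline.

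The endpoints serve Aim 2, which is "To qualitatively examine markers of disease burden". Its hypothesis, Hy2, concerns improvement "following the 24-week treatment course".

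Section 10 gives a different timing. It says that the primary outcome and overall symptom burden "will be assessed at weeks 20 and 24 (response at Week 24 only").

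The JAK2 endpoint in Section 4.2.2 counts patients "who achieve a >25% change in mutant allele burden from baseline to Week 24", while Hy2 predicts "reduced mutation allele burden".

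**The concern.** As written, a fall of one point on a single weekly form makes a patient a TSS responder, even if every other form is worse than baseline. A patient who worsens and leaves early still counts on the forms completed before leaving. The more often a fluctuating score is measured, the more likely it is to dip below its first value at least once. The proportion therefore reflects the number of looks as well as any drug effect. The same logic applies to palpated spleen length.

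The trial has no control arm in which the chance rate would show itself. A high reported proportion would be read as support for the symptom and spleen parts of Hy2, yet Hy2 concerns the state after 24 weeks and the endpoint does not.

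**Working it through.** **Number of looks.** Weekly forms from Day 8 to Day 169 number (169 - 8)/7 + 1 = 24. Scheduled visits after Day 1 number 8 weekly + 4 bi-weekly + 2 monthly = 14. For spleen this falls to 11 if Days 71, 99 and 141 are held by video (Sections 7.3.3 and 7.3.4).

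**Plan's own figure.** The documents state no rate, SD or correlation for these endpoints, so there is nothing to reproduce here. The Simon design for the primary endpoint does reproduce (9 then 11 patients, limits 1 and 4; exact alpha 0.0349, power 0.9018) and is not in question.

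**Result that needs no SD.** Suppose there is no drug effect and baseline and the k later scores are exchangeable without ties. Each of the k + 1 scores is then equally likely to be the lowest, so baseline is lowest with probability 1/(k + 1) and

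P(at least one later score below baseline) = k/(k + 1).

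- 24 weekly forms: 24/25 = 96.0%
- 14 visits: 14/15 = 93.3%
- Weeks 20 and 24 only: 2/3 = 66.7%
- Week 24 only: 1/2 = 50%; ties can only lower this
- a patient who leaves after 4 forms: 4/5 = 80%

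**Illustration with correlated, whole-point TSS.** All inputs are assumptions: patient mean 15, first-order autoregressive weekly noise, floor at 0, no drug effect, 200,000 simulated patients per setting.

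| Weekly SD | Autocorrelation | Any fall, 24 forms | Any fall, 14 visits | Any fall at Week 24 |
|---|---|---|---|---|
| 1 | 0 | 89.6% | 84.4% | 36.4% |
| 1 | 0.95 | 67.2% | 64.4% | 34.1% |
| 1 | 0.99 | 43.6% | 41.1% | 24.3% |
| 3 | 0 | 94.5% | 91.1% | 45.3% |
| 3 | 0.95 | 83.9% | 82.2% | 44.5% |
| 5 | 0.8 | 91.9% | 90.0% | 47.3% |
| 5 | 0.99 | 79.1% | 77.5% | 43.8% |

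A wider grid used means 10 to 30, between-patient SD 0 to 15, within-patient SD 3 to 8 and autocorrelation 0 to 0.8. It gave 67% to 96% with 24 forms, and 1% to 20% for a fall of 10 points or more at Week 24. The 67% end needs some patients with a negative true mean; truncating true means at 0 gives 81% or more. At autocorrelation 0.95 the grid reached down to 61%, and at 0.99 to 52%. The 41% to 44% in the table needs very small, almost perfectly correlated noise.

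**Spleen.** The any-visit set contains Week 24, so its rate cannot be below the Week 24 rate. How far above depends on assumed palpation error and rounding. With lengths recorded to 1 cm, independent error and 14 measurements:

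| True lengths | Error SD (cm) | Any visit | Week 24 | Ratio |
|---|---|---|---|---|
| spread evenly, 6-12 cm | 0.2 | 34.8% | 11.3% | 3.08 |
| spread evenly, 6-12 cm | 0.5 | 70.7% | 25.6% | 2.76 |
| spread evenly, 6-12 cm | 1.0 | 84.8% | 36.6% | 2.32 |
| on whole centimetres | 0.2 | 8.8% | 1.2% | 7.2 |
| on whole centimetres | 0.5 | 78.4% | 24.4% | 3.22 |

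True lengths close to the 5 cm cut with large error bring the ratio down to about 1.6.

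**The case against.** The strongest reply is that little hangs on these endpoints. Aim 2 is declared qualitative, with no test, alpha, reference rate or decision rule. A demanding symptom criterion (a fall of at least 10 points, lasting 12 weeks) already sits in Appendix 12.4 and feeds the primary endpoint. The spleen subset may hold very few patients. All of this stands and limits the severity. It does not rescue the definitions, because a proportion of responders will still be reported and read against Hy2.

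Second, the parenthesis in Section 10 may already restrict symptom response to Week 24, which would remove the repeated looks for TSS. It may equally refer to the primary outcome alone. A reader might infer a flat contradiction, but the wording does not settle that. What is certain is that Weeks 20 and 24 do not match any time point. Under either reading of Section 10, Section 4.2.2 still sets no size threshold.

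Third, the simulated rates rest on inputs that the documents do not supply. This is right. A reader might take 96% as the expected TSS rate, or infer that most spleen responders would arise by chance. Neither is shown. With small palpation error the spleen rate can be low, and the Study Synopsis asks for the same technique and ideally the same examiner.

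Fourth, a fixed Week 24 comparison is still uncontrolled. Patients stop other ET therapy before dosing (inclusion criterion 12), and Section 3.1 says that hydroxyurea worsens symptoms, so scores could change without any effect of the study drug. This also stands: the fix removes the inflation from repeated looks, not the lack of a comparator.

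**Conclusion.** The concern holds for the definitions in Section 4.2.2. The 96% and 93% are exact for exchangeable, untied scores with no drug effect, against at most 50% for any fall at Week 24. Outside that case, TSS rates of roughly 50% to 96% (lower only in the extreme settings shown) and spleen ratios of about 1.6 to 7 are illustrations, not bounds. For spleen, the finding that needs no assumed error is only that the any-time rate is at or above the Week 24 rate.

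The two proportions therefore cannot by themselves support the symptom and spleen parts of Hy2. A reader might go further and conclude that the trial's main result is compromised. The documents do not support that: the primary endpoint, the marrow endpoint and the sample size do not depend on these proportions. The JAK2 wording is a separate, small defect: read literally, it counts rises in allele burden.

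**What to change.** No new visit or measurement is needed, because Section 7.3.4 requires Day 169 in person with all assessments.

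- **TSS.** Make the Week 24 change from one named pre-dose form the main symptom summary, as a mean change with a confidence interval. Report how many patients have a Week 24 score and why others do not.
- **Supporting TSS result.** Show the proportion with a fall of 10 points or more, labelled as the Appendix 12.4 size criterion without its 12-week durability, with the number whose baseline is 10 or more. It should not be the main measure: patients with a baseline under 10 cannot meet it, and in the simulated settings that was up to about half of them.
- **Sensitivity.** Repeat that proportion with missing Week 24 scores counted as non-response. For example, 6 responders with 4 missing is 6/20 = 30% instead of 6/16 = 37.5%.
- **Spleen.** Report the Week 24 change in length in the >5 cm subset, with the number measured.
- **Any-time proportions.** Keep both, marked as descriptive only.
- **Timing.** Reconcile Section 4.2.2 with Section 10 on symptom burden.
- **JAK2.** Replace change with reduction, and report increases separately.

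The cost is that reported proportions will be lower. Because the trial is open-label and the protocol is at Version 13, the change must be dated and disclosed as made after earlier versions.
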